4.6.5. Electrocardiograms

Treatment-emergent qualitative ECG abnormalities are defined as qualitative abnormalities that first occurred after baseline. Qualitative abnormal ECGs will be recorded as adverse events. A listing of abnormal qualitative ECGs will be created.

4.6.6. Clinical Laboratory Evaluation

For Lp(a), only nmol/L will be reported. All other laboratory data will be reported in both CN and SI units. Limits from the performing lab will be used to define low (L) and high (H). Descriptive summaries by treatment and by nominal visit will be provided for the baseline and postbaseline values as well as the change from baseline values.

Observed and change from baseline values for each visit may be displayed in plots for participants who have both a baseline and at least 1 postbaseline planned measurement. Baseline will be the last non-missing observation prior to taking first study drug. Unplanned measurements will be excluded from plots.

A shift table will be provided including unplanned measurements. The shift table will include the number and percentage of participants within each baseline category (low, normal, high, or missing) versus each postbaseline category (low, normal, high, or missing) by treatment. The proportion of participants shifted will be compared between treatments using Fisher's exact test.

For qualitative laboratory analytes, the counts and percentages of participants with normal and abnormal values will be summarized by treatment.

A listing of abnormal findings will be created for laboratory analyte measurements, including qualitative measures. The listing will include participant identification, treatment group, laboratory collection date, study day, analyte name, and analyte finding.

The MMRM model as described in Section 4.1.2.1 or ANCOVA (if MMRM model is not applicable due to single postbaseline measurement) will be used for the analysis during the treatment period for the continuous measurements for selected lab tests.

4.6.7. Additional Safety Assessments

4.6.7.1. Hepatobiliary Disorders

The counts and percentages of participants with treatment-emergent potentially drug-related hepatobiliary disorders will be summarized by treatment using the PTs nested within Standardized MedDRA Queries (SMQs). Detailed search criteria can be found in Appendix 6 (Section 6.6).

4.6.7.1.1. Liver Enzymes

Analyses for laboratory analyte measurements are described in Section 4.6.6. This section describes additional analyses of liver enzymes.

Hepatic labs include alanine aminotransferase (ALT), aspartate aminotransferase (AST), total bilirubin (TBL), direct bilirubin (DBL), serum alkaline phosphatase (ALP), international normalized ratio (INR), and gamma-glutamyl transferase (GGT). When criteria are met for hepatic evaluations, investigators will conduct close monitoring of hepatic symptoms and liver

tests, perform a comprehensive evaluation for alternative causes of abnormal liver tests, and complete follow-up hepatic safety electronic case report form (eCRFs).

The following will be analyzed for hepatic safety (Table EKBC.4.5):

Table EKBC.4.5. Summary Tables and Figures Related to Hepatic Safety

Analysis	Population or Analysis Set
 Abnormal Postbaseline Categories – Hepatic Safety Parameters ALT The number and percentage of participants with a measurement greater than or equal to 1×, 3×, 5×, 10×, and 20× the performing lab ULN during the treatment period for all participants with a postbaseline value. AST The number and percentage of participants with a measurement greater than or equal to 1×, 3×, 5×, 10×, and 20× the performing lab ULN during the treatment period for all participants with a postbaseline value. ALP The number and percentage of participants with a measurement greater than or equal to 2× and 3× the performing lab ULN during the treatment period will be summarized for all participants with a postbaseline. TBL The number and percentage of participants with a measurement greater than or equal to 2×, 5×, and 8× the performing lab ULN during the treatment period will be summarized for all participants with a postbaseline value. DBL The number and percentage of participants with a measurement greater than or equal to 2× and 5× the performing lab ULN during the treatment period will be summarized for all participants with a postbaseline value. DBL The number and percentage of participants with a measurement greater than or equal to 2× and 5× the performing lab ULN during the treatment period will be summarized for all participants with a postbaseline value. DBL The number and percentage of participants with a measurement greater than or equal to 2× and 5× the performing lab ULN during the treatment period will be summarized for all participants with a postbaseline value. 	SS
Hepatocellular Drug-Induced Liver Injury Screening Plot (TBL vs. ALT or AST)	SS
Hepatocellular Drug-Induced Liver Injury Screening Table	SS
Cholestatic Drug-Induced Liver Injury Screening Plot (TBL vs. ALP)	SS
Cholestatic Drug-Induced Liver Injury Screening Table	SS
Participant profiles will be created for participants meeting criteria for a comprehensive hepatic evaluation (as defined in the protocol). Participant profiles will include demographics, disposition, information collected on the hepatic safety CRFs (where applicable) and a display of study drug exposure, adverse events, medications, blood pressure, heart rate, and the liver -related measurements over time.	SS

Abbreviations: ALP = alkaline phosphatase; ALT = alanine aminotransferase; AST = aspartate aminotransferase; CRF = case report form; DBL = direct bilirubin; INR = international normalized ratio, GGT = gamma-glutamyl transferase; TBL = total bilirubin; ULN = upper limit of normal. Planned and unplanned measurements will be included. The measurements do not need to be taken at the same blood draw. Maximum baseline will be the maximum non-missing observation in the baseline period. The maximum value will be the maximum non-missing value from the postbaseline period.

The primary purpose of the screening plots is to identify participants whose data warrant further review. For these plots, symbols will be used to indicate the randomized treatment.

For individual participants of interest, participant profiles will be reviewed. The review will include which treatment the participant was taking over time, the changes in hepatic labs over time, and the temporal association with potential causes. The review of participant profiles will also include the identification of any potential Hy's law case or potential cholestatic liver injury case that could have been missed by focusing only on the maximum values when determining 30-day time associations.

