- 22. Lipoprotein apheresis within 3 months of Visit 1, or planned during the study.
- 23. Treatment with another investigational drug, biological agent, or device within 1 month of Visit 1, or 5 half-lives of investigational agent, whichever is longer.
- 24. Treatment with any investigational oligonucleotide or siRNA within 9 months of Visit 1.

Prior/Concurrent Clinical Study Experience

25. Are currently enrolled in any other clinical study involving an investigational product or any other type of medical research judged not to be scientifically or medically compatible with this study.

Diagnostic Assessments

- 26. Clinically significant abnormalities in screening laboratory values that would render a participant unsuitable for inclusion in the opinion of the investigator.
- 27. Any of the following abnormalities:
 - a. estimated glomerular filtration rate (eGFR) <30 mL/min/1.73 m²
 - b. alanine aminotransferase (ALT) or aspartate aminotransferase (AST) >3.0x upper limit of normal (ULN)
 - c. bilirubin > 1.5x ULN, except for participants diagnosed with Gilbert's syndrome

Other Exclusions

- 28. Are Lilly employees, or are employees of any third party involved in a study that requires exclusion of their employees.
- 29. Are investigator site personnel directly affiliated with this study and/or their immediate families. Immediate family is defined as a spouse, parent, child, or sibling, whether biological or legally adopted.
- 30. Are pregnant, or intend to become pregnant or to breastfeed during the study.
- 31. Are, in the judgment of the investigator, actively suicidal and therefore deemed to be at significant risk for suicide.

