8.2.3. Hepatic Safety Close hepatic monitoring

Laboratory tests (Appendix 10.6), including ALT, AST, ALP, TBL, direct bilirubin (D. Bil), gamma-glutamyltransferase (GGT), and creatine kinase (CK), should be repeated within 48 to 72 hours to confirm the abnormality and to determine if it is increasing or decreasing, if 1 or more of these conditions occur:

If a participant with baseline results of	develops the following elevations:
ALT or AST <1.5x ULN	ALT or AST ≥3x ULN
ALP <1.5x ULN	ALP ≥2x ULN
TBL <1.5x ULN	TBL ≥2x ULN, except for participants with Gilbert's syndrome
ALT or AST ≥1.5x ULN	ALT or AST ≥2x baseline
ALP ≥1.5x ULN	ALP ≥2x baseline
TBL ≥1.5x ULN	TBL ≥1.5x baseline, except for participants with Gilbert's syndrome

If the abnormality persists or worsens, clinical and laboratory monitoring, and evaluation for possible causes of abnormal liver tests should be initiated by the investigator in consultation with the Lilly-designated medical monitor. At a minimum, this evaluation should include physical examination and a thorough medical history, including symptoms, recent illnesses (for example, heart failure, systemic infection, hypotension, or seizures), recent travel, history of concomitant medications (including over the counter), herbal and dietary supplements, history of alcohol drinking and other substance abuse.

Initially, monitoring of symptoms and hepatic biochemical tests should be done at a frequency of 1 to 3 times weekly, based on the participant's clinical condition and hepatic biochemical tests. Subsequently, the frequency of monitoring may be lowered to once every 1 to 2 weeks, if the participant's clinical condition and laboratory results stabilize. Monitoring of ALT, AST, ALP, and TBL should continue until levels normalize or return to approximate baseline levels.

Comprehensive hepatic evaluation

A comprehensive evaluation should be performed to search for possible causes of liver injury if 1 or more of these conditions occur:

If a participant with baseline results of	develops the following elevations:
ALT or AST <1.5x ULN	ALT or AST ≥3x ULN with hepatic signs/symptoms ^a , or ALT or AST ≥5x ULN
ALP <1.5x ULN	ALP ≥3x ULN
TBL <1.5x ULN	TBL ≥2x ULN (except for participants with Gilbert's syndrome)
ALT or AST ≥1.5x ULN	ALT or AST $\ge 2x$ baseline with hepatic signs/symptoms ^a , or ALT or AST $\ge 3x$ baseline
ALP≥1.5x ULN	ALP ≥2x baseline
TBL≥1.5x ULN	TBL ≥2x baseline (except for participants with Gilbert's syndrome)

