4.1.1. Definition of Baseline

Unless specified otherwise, baseline is defined as the last non-missing measurement recorded on or before the randomization visit (Visit 2), prior to the first dose of intervention, which in most cases will be the measurement recorded at Week 0 (Visit 2). For the safety related parameters, the definition of baseline and postbaseline are specified in Table EKBC.4.2.

Study Period/	Particinant Population	Baseline Observations	Postbaseline Observations
Analysis Type	i articipant i opulation	Daschile Observations	i ostbasenne observations
1.1) Treatment-	All randomized participants	The baseline period is	Starts at or after the first
Emergent Adverse	who are exposed to at least	defined as the start of	dose of study drug and ends
Events (SS)	1 dose of study drug	screening and ends prior to	at the conclusion of the
		the first dose of study drug.	study period.
1.2) Treatment-	All randomized participants	Baseline will be all	Postbaseline will be defined
Emergent Abnormal	who are exposed to at least	scheduled and unscheduled	as above (1.1). All
Labs and Vital Signs	1 dose of study drug who	measurements recorded	scheduled and unscheduled
(SS)	have a normal baseline	during the baseline period as	measurements will be
	(with respect to the direction	defined above (1.1).	included.
	being analyzed) and a post-		
	baseline observation		
1.3) Change from	All randomized participants	The last scheduled non-	Postbaseline will be defined
Last Baseline to each	who are exposed to at least	missing assessment	as above (1.1). Only
postbaseline week	1 dose of study drug and	recorded prior to the first	scheduled visits will be
and to last	have a baseline and at least	dose of study treatment	included. The early
postbaseline for Labs,	1 post-baseline observation	during the baseline period	discontinuation visits are
Vital Signs (SS)		defined above (1.1).	considered scheduled visits.

 Table EKBC.4.2.
 Baseline and Postbaseline Definitions for Safety Analyses

Abbreviations: ED = early discontinuation; SS = safety set.

Note: for the continuous analysis of clinical laboratory tests, unscheduled measurements are excluded from analysis to reduce bias. The early discontinuation visits are considered scheduled visits.

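### The liver-test counts in SAP Table EKBC.4.5 ignore baseline, so persistent or barely changed entry elevations can dilute arm differences in the low-threshold ALT/AST rows, the ALP and direct bilirubin rows, and the total bilirubin rows in Gilbert's syndrome

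*SAP*

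**What the plan says.** **The table.** In SAP section 4.6.7.1.1, the ALT and AST rows of Table EKBC.4.5 count participants with "a measurement greater than or equal to 1×, 3×, 5×, 10×, and 20× the performing lab ULN during the treatment period". The ALP row uses values "greater than or equal to 2× and 3× the performing lab ULN during the treatment period will be summarized". The total bilirubin (TBL) row uses 2x, 5x and 8x ULN, and the direct bilirubin (DBL) row 2x and 5x. The ALT and AST rows refer each multiple to "the performing lab ULN during the treatment period for all participants with a postbaseline value", and in the other rows too anyone with a postbaseline value can be counted. The footnote says "Maximum baseline will be the maximum non-missing observation in the baseline period", but no visible count row uses that quantity.

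**Entry.** Protocol section 5.2, criterion 27b, excludes "alanine aminotransferase (ALT) or aspartate aminotransferase (AST) >3.0x upper limit of normal (ULN"), so values up to and including 3.0x are admitted. Criterion 27c excludes bilirubin above 1.5x ULN, "except for participants diagnosed with Gilbert's syndrome". Criterion 27 gives no limit for ALP or DBL. Criterion 26 lets the investigator exclude a participant for clinically significant screening laboratory abnormalities.

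**Protocol hepatic monitoring.** Section 8.2.3 splits participants at a baseline of 1.5x ULN. Below it, thresholds are ULN multiples, for example "TBL ≥2x ULN, except for participants with Gilbert's syndrome". At or above it, thresholds are multiples of the participant's own baseline.

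**Other outputs.** The treatment-emergent laboratory analysis (SAP Table EKBC.4.2, row 1.2) is restricted to participants who "have a normal baseline" in the direction analysed. SAP section 4.6.6 plans a shift table in low, normal, high and missing categories, and change-from-baseline summaries. Section 4.6.7.1.1 adds screening plots and participant profiles.

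**The concern.** A fixed ULN multiple marks an on-study change only if participants start below it. Here some may start at or just under several of the cut-offs. A participant who enters with ALT at 1.5x ULN and stays there is counted at 1x ULN or more. A participant with Gilbert's syndrome whose TBL stays at 2.2x ULN is counted at 2x or more.

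These are the plan's main by-arm hepatic counts at graded thresholds. Both documents justify the sample size by the amount of safety data it yields, and protocol section 4.2 describes the study as Phase 3 enabling. Background cases in every arm shrink the visible contrast between a dose and placebo. In the smallest arm, one or two such cases can look like an imbalance.

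**Working it through.** The plan states no figure for this table, so there is none to reproduce. The check has three steps.

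**1. Which rows can a value admitted at entry already meet?**

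| Test | Entry limit | Rows that can be met | Rows that cannot |
|---|---|---|---|
| ALT, AST | at most 3.0x ULN | 1x; 3x only at exactly 3.0x | 5x, 10x, 20x |
| ALP | no numeric limit (criterion 26 only) | 2x, 3x | none by number |
| TBL, no Gilbert's | at most 1.5x ULN | none | 2x, 5x, 8x |
| TBL, Gilbert's | no numeric limit (criterion 26 only) | 2x, 5x, 8x | none by number |
| DBL | no limit of its own | 2x, 5x | none by number |

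The ALT/AST 3x row can also be reached by trivial drift. From 2.8x to 3.1x ULN is 3.1/2.8 = 1.11 times baseline. From 2.0x to 4.0x ULN is 4.0/2.0 = 2.0 times baseline, which meets the protocol's close-monitoring threshold for a raised baseline. Both participants fall in the same cell.

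The table above uses screening values. The SAP's baseline period runs to the first dose, so a pre-dose Visit 2 value could exceed the limit that the Visit 1 value met.

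**2. Does another by-arm count supply the missing split?**

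- The treatment-emergent analysis drops participants whose baseline is not normal.
- The shift table puts 1.2x staying at 1.2x ULN, and 1.2x rising to 8x ULN, in the same high-to-high cell.
- Change from baseline gives averages by visit, not counts.
- Screening-plot symbols identify randomized treatment only.
- Participant profiles follow the protocol's baseline-dependent criteria, but they are individual reviews, not counts by arm.

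**3. How large could the dilution be?** The documents give no baseline rates, so every rate below is an assumption. The figures apply to low-threshold rows only.

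Arm sizes: 233 x 1/7 = 33.3 for 10 mg and 233 x 2/7 = 66.6 for each other arm, taken as 33 and 67. One background case is 1/33 = 3.0% of the 10 mg arm.

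*ALT at 1x ULN or more.* Let b be the proportion raised at baseline, with 80% of these still raised after baseline in both arms. New elevations are 2% on placebo and 15% on a dose. The rate shown in each arm is 0.8b + (1 - b) x new rate. For b = 10%: placebo 0.08 + 0.9 x 0.02 = 0.098; dose 0.08 + 0.9 x 0.15 = 0.215; ratio 2.19. Power is by exact enumeration of two-sided Fisher tests at 0.05, with 67 per arm for the table and 67(1 - b), rounded, for normal baselines.

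| b | Background cases per 67 (67 x 0.8b) | Risk ratio shown (true 7.5) | Power, table as written | Power, normal baseline only |
|---|---|---|---|---|
| 0% | 0 | 7.5 | 72% | 72% |
| 5% | 2.7 | 3.1 | 51% | 68% |
| 10% | 5.4 | 2.2 | 38% | 64% |
| 20% | 10.7 | 1.6 | 24% | 57% |
| 30% | 16.1 | 1.4 | 16% | 47% |

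*A rarer low-threshold row, such as ALP at 2x ULN.* Assume new elevations of 1% versus 10%, and a proportion b per arm counted only because of baseline. The rate shown is b + (1 - b) x new rate. For b = 2%, 4%, 6% and 10%, the true risk ratio of 10 shows as 4.0, 2.7, 2.2 and 1.7. Power is 36%, 30%, 25% and 19% as written, against 47%, 45%, 43% and 40% when those participants are separated. It is 48% with no background.

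**The case against.** The strongest reply is that the plan already handles baseline where it matters. The table is headed as abnormal postbaseline values, not treatment-emergent ones. New ALT/AST elevations from a normal baseline are covered by the treatment-emergent analysis, which uses the most extreme baseline value (SAP section 4.1.2.3). Profiles are produced for everyone who meets the protocol's comprehensive hepatic evaluation criteria. Those criteria depend on baseline and exempt Gilbert's syndrome from the TBL thresholds. The hepatic safety CRF triggers in protocol section 8.2.3 also depend on baseline.

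Most of this stands, and it rules out three stronger readings that a reader might infer:

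- *Pre-existing elevations are reported as drug effects.* The heading does not say so, and randomization spreads such cases evenly across arms in expectation.
- *No count shows new elevations at 3x or 5x ULN.* For ALT/AST, a screening value that passed entry cannot meet 5x or above and meets 3x only at exactly 3.0x. TBL at 2x is likewise out of reach at entry without Gilbert's.
- *Worsening from a raised baseline cannot be seen at all.* Profiles show it participant by participant.

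It is also wrong to say that any ALP, or any bilirubin in Gilbert's, is admitted. There is no numeric limit, but criterion 26 applies.

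Two further cautions are fair. Table EKBC.4.5 asks for numbers and percentages only; a Fisher test would enter through the general rules in SAP section 4.1. The DBL row is repeated in the text available here, so the layout may be damaged. A baseline breakdown lost in this way cannot be excluded, and the source table should be checked.

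What survives is narrow: no planned by-arm count shows worsening by threshold among participants who entered with raised tests.

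**Conclusion.** The point holds for the ALT/AST 1x and 3x rows, the ALP and DBL rows, and the TBL rows in Gilbert's syndrome. It does not extend to ALT/AST at 5x to 20x, or to TBL at 2x and above without Gilbert's, as far as values that passed screening are concerned.

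The consequence is dilution of between-arm differences and possible chance imbalance, chiefly in the 33-participant arm. The documents do not support a claim of systematic bias against the drug or of mislabelling.

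The size cannot be fixed from the documents. In the illustrations, a true risk ratio of 7.5 shows as 3.1 to 1.4 when 5% to 30% enter with raised ALT. These results rest on assumed rates and on background cases behaving alike in both arms. In the rarer-event illustration power stays below 50% even after separation, so the gain is clearer description, not an adequately powered test. This is a low-cost improvement to the safety tables and does not affect the efficacy conclusions.

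**What to change.** Keep the all-participant rows of Table EKBC.4.5 and add:

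1. Each count split by maximum baseline, below 1.5x ULN versus at or above 1.5x ULN. This uses the footnote's definition and the protocol's own cut.
2. In the raised stratum, counts by arm at the close-monitoring multiples of baseline already in protocol section 8.2.3: ALT/AST at 2x or more, ALP at 2x or more, TBL at 1.5x or more. The SAP should name this set, because section 8.2.3 also holds a second one for comprehensive evaluation. This is tabulation only and changes no monitoring or stopping rule.
3. Participants with Gilbert's syndrome shown separately for TBL, identified from the medical history collected at Visit 1.

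One limit remains. Participants with a baseline between 1x and 1.5x ULN stay in the lower stratum, so the ALT/AST 1x row there still mixes new and persistent values. The treatment-emergent analysis remains the better source for that threshold.

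The cost is SAP wording, extra table rows and smaller denominators. No new data collection is needed.

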7.1. Discontinuation of Study Intervention

When necessary, a participant may be permanently discontinued from study intervention. If so, the participant will remain in the study to complete procedures for an ED visit and post-treatment follow-up, if applicable, as shown in the SoA.

A participant should be permanently discontinued from study intervention if

- the participant becomes pregnant during the study
- in the opinion of the investigator, the participant should permanently discontinue the study intervention for safety reasons
- if the investigator determines that a systemic hypersensitivity reaction has occurred related to study intervention administration, the participant may be permanently discontinued from the study intervention, and the sponsor's designated medical monitor should be notified. If the investigator is uncertain about whether a systemic hypersensitivity reaction has occurred and whether discontinuation of study intervention is warranted, the investigator may consult the sponsor
- the participant has an AE or an SAE or a clinically significant change in a laboratory value that, in the opinion of the investigator, merits discontinuation of study intervention and appropriate measures being taken
- if the participant experiences a hepatic event or liver test abnormality as specified in the liver chemistry stopping criteria (see Section 7.1.1), and
- HBV or HCV: The participant tests positive for HBV DNA (see Section 8.2.5) or tests positive for HCV RNA (Section 8.2.6).

Note: The HBV DNA result is to be confirmed if initial positive test result is positive but below the level of quantification. Prior to discontinuation of any immunomodulatory and/or immunosuppressive therapy, including study intervention, the participant is to be referred to, evaluated, and managed by a specialist physician with expertise in evaluation and management of viral hepatitis. The timing of discontinuation from study intervention relative to the initiation of any antiviral treatment for hepatitis is to be based on the recommendation of the consulting specialist physician, in conjunction with the investigator, and aligned with medical guidelines and standard of care.

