
Treatment contrast of interest: *difference in mean percent changes in Lp(a) between LY3473329 and placebo.*

Rationale for estimand: This Phase 2 study aims to study the efficacy of LY3473329 under the ideal condition that all participants adhere to the randomized treatment without initiating other medications known to impact Lp(a) levels.

A similar efficacy estimand will be used for the secondary and exploratory objectives.

Unless specified otherwise, safety assessments will be guided by an estimand comparing safety of LY3473329 doses with placebo irrespective of adherence to study intervention or initiation of new Lp(a) modifying medication, including data collected during the treatment period and safety follow-up.

Secondary estimand

For the primary endpoint, a secondary clinical question of interest is: What is the intervention difference in percent change from baseline in Lp(a) after 12 weeks of study intervention in participants who meet the inclusion criteria regardless of treatment discontinuation for any reason or initiation of other medications known to impact Lp(a) levels?

This question is addressed using the treatment-regimen estimand, which is described by the following attributes:

Population: participants who meet the enrollment criteria. Further details can be found in Section 5 of the study protocol of EKBC.

Endpoint: percent change from baseline to Week 12 in Lp(a).

Treatment condition: the randomized treatment. Further details on study interventions, and concomitant interventions can be found in Section 6 of the study protocol of EKBC.

The intercurrent events "intervention discontinuation for any reason" and "new initiation of any Lp(a) modifying medication" are addressed by the treatment-regimen strategy, and the potential

outcome of interest is the response in the efficacy measurement regardless of whether participants had adhered to the randomized treatment without using such medication.

Population-level summary: mean percent changes in Lp(a).

Treatment contrast of interest: difference in mean percent changes in Lp(a) between LY3473329 and placebo.

Rationale for estimand: this estimand aims to study the efficacy of LY3473329 that reflects the real-life behavior of the target population.

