2.1. Multiplicity Adjustment

Treatment comparisons will be performed for the primary objective at the full significance level of 0.05. No multiplicity adjustments will be made for the analysis of secondary and exploratory objectives.

3. Analysis Sets

This table defines the analysis population and datasets for the purposes of analysis.

Population	Description
Screened	All participants who sign the ICF.
Randomized	All participants who are randomly assigned to a treatment arm.
Efficacy Analysis Set (EAS)	Data obtained during treatment period from all randomly assigned participants who are exposed to at least 1 dose of double-blind study treatment. Excludes data after discontinuation of study drug or initiation of Lp(a) modifying medication.
Full Analysis Set (FAS)	Data obtained during the treatment period from all randomly assigned participants who are exposed to at least 1 dose of intervention, regardless of adherence to intervention or initiation of Lp(a) modifying medication.
Safety Analysis Set (SS)	Data obtained during the treatment period plus safety follow-up from all randomly assigned participants who are exposed to at least 1 dose of intervention, regardless of adherence to intervention or initiation of Lp(a) modifying medication.

Abbreviation: ICF = informed consent form.

4. Statistical Analyses

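### The liver-category rows of SAP Table EKBC.4.5 count treatment-period values only, although the table's title, denominator, analysis set and footnote all reach into safety follow-up

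*SAP*

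**What the plan says.** The first block of Table EKBC.4.5 (SAP Section 4.6.7.1.1) tabulates participants reaching given multiples of the ULN: 1, 3, 5, 10 and 20 for ALT and AST; 2 and 3 for ALP; 2, 5 and 8 for total bilirubin (TBL); 2 and 5 for direct bilirubin (DBL). The time window in the rows reads:

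- ALT and AST: "during the treatment period for all participants with a postbaseline value".
- ALP: "2× and 3× the performing lab ULN during the treatment period will be summarized".
- TBL: "2×, 5×, and 8× the performing lab ULN during the treatment period will be summarized for all participants with a postbaseline value". DBL is worded in the same way.

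The rest of the SAP sets a wider window for the same output:

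- The block's title calls these postbaseline categories.
- The analysis set is the SS, defined in SAP Section 3 as "Data obtained during the treatment period plus safety follow-up from all randomly assigned participants" with at least one dose, regardless of adherence.
- The table footnote admits planned and unplanned samples and states: "The maximum value will be the maximum non-missing value from the postbaseline period".
- Table EKBC.4.2 runs postbaseline from first dose to the end of the study period.
- The safety estimand in SAP Section 1.1 is described as "including data collected during the treatment period and safety follow-up".

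Protocol Section 1.3 makes treatment (Period III, which includes the ED visit) and post-treatment follow-up (Period IV, Visit 801) separate periods. For permanent discontinuation of study drug, Protocol Section 7.1 says that "the participant will remain in the study to complete procedures for an ED visit and post-treatment follow-up", where applicable.

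**The concern.** The numerator and denominator use different windows. A participant enters the denominator through any postbaseline value but enters the numerator only through a treatment-period value. A programmer who follows the row text and one who follows the footnote would produce different counts from the same data.

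The values in dispute are ones that the protocol requires. Clinical chemistry is scheduled at Visit 801. Under Protocol Section 8.2.3, abnormal liver tests are rechecked within 48 to 72 hours. If the abnormality persists or worsens, they are followed 1 to 3 times weekly at first, then possibly less often, until they normalize or approach baseline. Retests made after treatment ends, and any elevation first seen at Visit 801, belong to the SS and to the postbaseline period but fall outside the literal row text. A hepatic summary meant to serve a safety estimand that includes follow-up should not omit them by default.

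**Working it through.** No sample-size, power or alpha figure is involved. The check compares windows and then sizes the gap.

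**Scheduled samples.** The Schedule of Activities places postbaseline clinical chemistry for a completer at Visits 3, 4, 5, 6, 7 and 801, which is 6 samples. Visit 801 is in Period IV, so the rows exclude 1 of 6.

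**Time.** Treatment lasts up to 12 weeks, and Visit 801 is about 4 weeks after the last dose. For a stop at week s, observed postbaseline time is s + 4 weeks. The SAP gives no formal end to the treatment period, so two readings are needed.

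*Reading A, the period ends at last dose or the ED visit (taken as the same time here).* Excluded share = 4 / (s + 4).

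*Reading B, the period is a fixed 12 weeks.* Excluded share = max(0, s + 4 − 12) / (s + 4).

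| Stop at week | Observed weeks | Reading A | Reading B |
|---|---|---|---|
| 4 | 8 | 4/8 = 50% | 0% |
| 8 | 12 | 4/12 = 33% | 0% |
| 12 (completer) | 16 | 4/16 = 25% | 4/16 = 25% |

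The completer row is the same under both readings. The early-stop rows are not.

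**Which reading the text favors.** The exposure calculation in SAP Section 4.6.1 ties the treatment period to the last dose, which points to A. The efficacy set in SAP Section 3 starts from treatment-period data and then removes data after drug discontinuation. That step would be largely redundant if the period ended at discontinuation, so it points to B. The question is open.

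**Illustration with assumed values.** A participant stops at Week 8 with ALT 4 times ULN and peaks at 12 times ULN ten days later, at week 8 + 10/7 = 9.4. Under A the table counts this participant at the 1 and 3 multiples and misses 5 and 10. Under B all four are counted. The postbaseline maximum in the footnote is 12 times ULN under either reading.

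**Weight of one participant.** 233 × 1/7 = 33.3 on 10 mg and 233 × 2/7 = 66.6 in each other arm. 1/33.3 = 3.0% and 1/66.6 = 1.5%. This is a scale, not a forecast: the documents give no expected rate of post-treatment liver elevations.

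**The case against.** The strongest reply is that the table nearly corrects itself. Its title, set, denominator and footnote all say postbaseline, and a sensible programmer could use that window. This is fair, but the limit is repeated for all five analytes, so a literal reading is at least as defensible.

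A reader might infer that participants stopped for liver injury always lose their peak. The documents do not support that. Under a fixed 12-week reading, many such peaks are counted. The ED visit belongs to Period III, so a peak seen there is counted. Protocol Section 7.1.1 also allows interruption, with possible resumption, and an interrupted participant may remain within the treatment period.

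A reader might also infer that a first elevation at Visit 801 goes unseen. It does not. It can appear in the shift table and the abnormal-findings listing (SAP Section 4.6.6), and in the hepatocellular and cholestatic screening plots and tables, which use the SS with no treatment-period limit. Profiles of participants who meet the criteria for comprehensive hepatic evaluation show liver measurements over time. Nor does the SAP call this block its main hepatic table; the section presents it among additional analyses, with no test or decision rule attached.

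These points limit the consequence. They do not remove the mismatch, because the shift table uses only low, normal and high, and the SAP specifies counts at these ULN multiples nowhere else.

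**Conclusion.** The point holds as an internal contradiction with a bounded effect. On the row wording, a completer's Visit 801 chemistry and any post-treatment liver retests are not counted under either reading of the treatment period. Loss of later peaks in participants who stop early is conditional: it occurs if the period ends at last dose or the ED visit, and largely disappears if the period is a fixed 12 weeks. A serious post-treatment elevation would not vanish from the hepatic review as a whole. But the category table could understate it, and could disagree with the screening plots about the same participant. The time shares assume Visit 801 at exactly 4 weeks after last dose and no observation beyond it. The change is worth making before unblinding, because the count now depends on an undefined term.

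**What to change.** In every ALT, AST, ALP, TBL and DBL row of Table EKBC.4.5, replace the treatment-period limit with the postbaseline period, stated as first dose to end of study participation, with scheduled and unscheduled samples included. This matches the SS, the footnote and Table EKBC.4.2, and puts numerator and denominator on one window. If an on-treatment count is also wanted, add it as a separate labelled column and define when the treatment period ends for participants who stop early.

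The cost is a SAP wording change and the matching table shell. It needs no new data and does not affect sample size, power or alpha.
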